### 5.5.2.3 Descriptive Statistics

Results of CNR from both unenhanced and contrast enhanced SI measurements will be presented at subject level (mean by subject) for each off-site reader and each dose of P03277 by period and combined periods 1 and 2 according to the contrast agent group.

By-site summaries will be produced to look for potential disparities among the sites (center effect). The presentation will be limited to descriptive statistics of contrast enhanced SI measurements in total. The p-values will not be reported for the by-site summaries.

Descriptive statistics of CNR from contrast enhanced SI measurements in total will be presented at subject level (mean by subject) for each off-site reader according to the contrast agent group and magnetic field: 1.5T or 3.0T.

Every descriptive analyses will be performed using the FAS restricted to patients with CNR data at both MRIs. Global descriptive statistics will be performed also using the PPS for matching lesions only.

The tables that will be displayed are detailed in Section 6.1.2.1.2.

CONFIDENTIAL	FORM	
STATISTICAL ANALYSIS PLAN N° GDX-44-004		Page 32 / 60
VERSION 1.0      DATED: 09JAN2018		

#### 5.5.2.4 Sensitivity Analysis on Subjects With Region of Interest Similarly Placed in MRI 1 and MRI 2

The primary analysis will be repeated per reader using the PPS for matching lesions only on lesions with ROI similarly placed in MRI 1 and MRI 2 according to the lesion tracker.

The table that will be displayed is detailed in Section 6.1.2.1.2.

### 5.5.3. Additional analyses of primary criterion

### 5.5.3.1 Dose/Response Relationship

The relationship between doses and CNR will be explored by two modeling approaches on all data observed under P03277. On the contrary to previous analyses, all subjects from the FAS with data under P03277 will be taken into account in the analysis, even if they had no MultiHance® in MRI 2. The following models will be performed considering the dose as a continuous variable:

- The *linear model* whose use is justified by the fact that it is the easiest approach needing no *a priori* knowledge of the pattern of relationship between dose and response.
- The *Emax model*, linear in log-dose, which may also be adequate based on existing data of CNR with P03277.

These analyses will be performed for the 3 off-site readers independently.

The linear model fits the dose/response function  $g(\text{dose})$  according to the following formula:

$g(\text{dose}) = E0 + \delta * \text{dose}$ , where  $E0$  is the response at baseline (i.e., absence of dose) and  $\delta$  is a slope factor.

The SAS® procedure used for these analyses will be the following:

```
proc reg data=XXX;  
  model eval =dose;  
  output out=XXX predicted=xx;  
run;
```

The 4-parameter  $E_{max}$  model fitting the dose/response function  $g(dose)$  according to the following formula will be used:

$$g(\text{dose}) = E_0 + (E_{\text{max}} * \text{dose}^{\lambda}) / (E_{\text{D50}}^{\lambda} + \text{dose}^{\lambda})$$

where  $E_0$  is the response at baseline (i.e., absence of dose),  $E_{\max}$  is the asymptotic maximum dose effect (maximum effect attributable to the contrast agent),  $D_{50}$  is the dose which produces 50% of the maximal effect and  $\lambda$  is a slope factor.

CONFIDENTIAL	FORM	
	STATISTICAL ANALYSIS PLAN N° GDX-44-004	
	VERSION 1.0      DATED: 09JAN2018	Page 33 / 60

The SAS® procedure used for these analyses will be the following:

```

proc nlin data = XXX;
  parms E0 = xxx Emax = xxx ED50 = xxx lambda = xxx;
  /* Initial parameters may be estimated based on study data; in particular, lambda may be retrieved from
     the estimated slope parameter in proc reg above */
  model eval = E0 + (Emax * dose** lambda) / (ED50** lambda + dose** lambda);
  output out=XXX predicted=xx;
run;

```

Results from these models will be displayed in tables containing estimates and in figures:

- Dose on X axis.
- CNR on Y axis.
- Adjusted line (linear model) or curve ( $E_{max}$  model).

The tables and figures that will be displayed are detailed in Section 6.1.2.1.3.

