#### ***7.2.6 P03277 dose / response relationship for CNR and lesion visualization variables***

The relationship between dose and response will be evaluated graphically based on mean profile. Depending on the graphical results, a more complex model including study drug dose (as continuous variable) could be fitted to evaluate the relationship between dose and CNR increase.

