#### Secondary analyses of the primary criterion

- **FAS analysis**
  - The primary analysis will be repeated using the FAS.
- **Overall analysis**
  - The primary analysis will be repeated by pooling together all off-site readers using the FAS and the PPS.
- **Centre Effect**
  - By-site summaries will be produced to look for potential disparities among the sites (center effect) using the FAS and the PPS. The p-values will not be reported for the by-site summaries.
- **Dose/response evaluation**
  - The relationship between doses of P03277 and response will be evaluated graphically based on mean profile during the study using the FAS and the PPS.
  - Depending on the graphical results, a more complex model including doses of P03277 (as continuous variable) could be fitted to evaluate the relationship between doses and CNR increase.

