### 3.4. Adjustment for covariates

The pre CNR measurement for unenhanced lesions (baseline value) will be included as covariate in the statistical models for the primary and supportive analyses of the primary criterion.

The stratification factor (brain metastasis at screening) will not be included as covariate in the statistical models. Indeed, it was judged as having no impact on the primary criterion. However, the analysis of number of lesions will be provided only on the subset of subjects with brain metastasis at screening.

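### The CNR dose-response fits omit the subject's own MultiHance CNR, pre-contrast CNR and period; this costs precision but does not bias the slope

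*SAP*

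**What the plan says.** SAP 5.5.3.1 sits under the additional analyses of the primary criterion. It states that "The relationship between doses and CNR will be explored by two modeling approaches on all data observed under P03277". FAS subjects with a P03277 value enter "even if they had no MultiHance® in MRI 2". The linear model is PROC REG with the statement "model eval =dose". The second model is PROC NLIN with a four-parameter Emax function of dose alone. Each is fitted per off-site reader, and the figures put CNR on the vertical axis.

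The section does not define the response variable. I read it as post-contrast CNR, because of the axis label and because SAP 5.5.1.3 uses the same variable name beside a separate baseline term.

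The primary model in SAP 5.5.1.3 contains contrast agent, period, pre-contrast CNR and a random subject effect. SAP 3.4 commits the pre-contrast covariate only to the primary and supportive analyses, so the additional analyses are not covered.

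Protocol 7.2.6 says that a model might be "fitted to evaluate the relationship between dose and CNR increase". Protocol 12.3 says that one "could be fitted to evaluate the relationship between doses and CNR increase". Neither place says what the increase is measured against. The secondary objective (Protocol 2.2, SAP 1.1) refers simply to dose/response for CNR.

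**The concern.** P03277 dose is a parallel-group factor, so any dose-response fit compares different people. CNR is scaled by background noise. The trial pools 1.5T and 3T scanners from any manufacturer (Protocol 9.2.1), and the SAP plans to describe CNR by field strength. The same equipment is mandatory for both of a subject's examinations. The MultiHance CNR, always at one dose, therefore carries information about that subject's scanner and disease. A fit without it leaves this variation in the residual.

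Dose/response for CNR is a stated secondary objective. SAP 5.5.1.5 chooses the dose on primary and secondary criteria, and allows a dose not shown superior to be recommended. A curve with avoidable noise could then inform the choice.

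**Working it through.** **The plan's own figure.** The documents state no precision or power for the dose-response fits. Their only related figure is 50 evaluable subjects per dose for at least 90% power in the primary comparison, with SD 3.01 (Protocol 8). It cannot be reproduced, because the mean MultiHance CNR to which the 30% applies is not given. Solving backwards for 90% power at n = 50 with the exact t-test gives:

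| Reading of 3.01 | One-sided alpha | Implied difference | Implied MultiHance mean (difference / 0.30) |
|---|---|---|---|
| unpaired, SD of CNR | 0.025 | 1.97 | 6.57 |
| unpaired, SD of CNR | 0.025/4 = 0.00625 | 2.31 | 7.71 |
| paired, SD of the difference | 0.025 | 1.41 | 4.69 |
| paired, SD of the difference | 0.00625 | 1.66 | 5.54 |

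The documents therefore do not settle which SD 3.01 is. This matters below for absolute standard errors but not for ratios.

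**Linear slope as coded.** Inputs: doses 0.025, 0.05, 0.1 and 0.2 mmol/kg, 50 subjects each, and 3.01 taken as the between-subject SD of CNR (assumption).

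- Mean dose = 0.375/4 = 0.09375.
- Sum of squared deviations = 0.06875² + 0.04375² + 0.00625² + 0.10625² = 0.01797.
- Sxx = 50 × 0.01797 = 0.898.
- Slope SE = 3.01/√0.898 = 3.18 CNR units per mmol/kg.
- 95% half-width over the tested range of 0.175 mmol/kg = 1.96 × 3.18 × 0.175 = 1.09 CNR units.

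**Using the MultiHance CNR.** Let rho be the within-subject correlation of the two CNR values, with equal variances. The documents give no value, so a range is shown. Relative to the coded fit, the slope variance is multiplied by 1 - rho² with MultiHance CNR as a covariate, and by 2(1 - rho) if the response is the simple difference.

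| rho (assumed) | Covariate: variance factor | Reduction | SE | Difference: variance factor | SE |
|---|---|---|---|---|---|
| 0 | 1.00 | 0% | 3.18 | 2.00 | 4.49 |
| 0.3 | 0.91 | 9% | 3.03 | 1.40 | 3.76 |
| 0.5 | 0.75 | 25% | 2.75 | 1.00 | 3.18 |
| 0.7 | 0.51 | 49% | 2.27 | 0.60 | 2.46 |
| 0.9 | 0.19 | 81% | 1.38 | 0.20 | 1.42 |

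Below rho = 0.5 the simple difference is worse than the coded fit. In this large-sample formula the covariate form never is.

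**Check for bias.** The simulation used 3,000 trials per correlation, 50 subjects per dose, normal data and a true slope of 20. Mean slope (empirical SE):

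| rho | Dose only | Difference | Covariate |
|---|---|---|---|
| 0.3 | 19.92 (3.16) | 19.98 (3.75) | 19.94 (3.03) |
| 0.5 | 19.83 (3.22) | 19.94 (3.25) | 19.88 (2.83) |
| 0.8 | 19.95 (3.20) | 19.98 (1.98) | 19.97 (1.89) |

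All three recover the slope; only the spread differs. No calculation was made for the Emax model, or for the gain from pre-contrast CNR and period.

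**The case against.** The best defence is that the within-subject question is already answered elsewhere. SAP 5.5.1.1 to 5.5.1.3 estimate P03277 minus MultiHance at each dose with a 95% confidence interval and plot the differences against dose. The protocol gives intra-subject comparison on the primary criterion as the reason for the crossover. The dose-response fits are exploratory, carry no alpha and keep subjects without a MultiHance scan on purpose. All of this stands. It limits the point to the fitted curve, which does not carry the control between or across the tested doses.

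A reader might infer more from the code, in four ways.

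- **The curve is biased, or chance imbalance distorts it.** Dose is randomised, so imbalance is sampling error and is already in the SE. The simulation shows no bias.
- **The SAP contradicts the protocol.** The protocol makes the model optional and leaves the increase undefined. It could be over MultiHance, over pre-contrast CNR, or with rising dose. The SAP does follow the wording of the secondary objective. What remains is an undefined term, and SAP Section 4 does not say how it was resolved.
- **The brain-metastasis stratum must be added.** SAP 3.4 says that "The stratification factor (brain metastasis at screening) will not be included as covariate in the statistical models", having judged it to have no impact on the primary criterion. Nothing in the documents shows an effect on CNR, and randomisation is stratified on it.
- **The gain is several-fold.** A gain worth 1/0.19 = 5.3 times the subjects needs rho = 0.9; at rho = 0.3 it is 1/0.91 = 1.1 times.

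It is also fair to say that the Emax model already has four parameters for four doses, so added covariates may prevent convergence.

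**Conclusion.** The concern holds as a matter of precision. The dose-response fits leave out three collected quantities that could sharpen them. The MultiHance CNR alone would reduce the linear slope variance by 0% to 81% over assumed correlations of 0 to 0.9. The true correlation is undocumented, so no single figure can be claimed.

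The SE of 3.18 holds only if 3.01 is the between-subject SD of CNR. If it is the SD of the paired difference, the coded slope SE is 3.18/√(2(1 - rho)), which is 2.25 at rho = 0 and 7.10 at rho = 0.9. The percentage reductions do not change.

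It does not follow that the trial cannot compare the two agents by dose: that contrast is planned at all four doses. The Holm-controlled primary test is unaffected. This is a worthwhile, inexpensive improvement to a secondary objective that may inform dose choice, and not a flaw in the trial's main inference.

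**What to change.** In SAP 5.5.3.1:

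- Make the main linear fit, in subjects with both scans, regress P03277 CNR on dose with same-reader MultiHance CNR, pre-contrast CNR and period as covariates.
- Do the same for the Emax model where it converges, and state in advance what is reported if it does not.
- Use the covariate form, not the simple difference, because the correlation is unknown and the difference loses precision below 0.5.
- Keep the planned unadjusted P03277-only fit on all eligible FAS subjects as a sensitivity analysis.
- Define the response and say which CNR increase, as named in Protocol 7.2.6 and 12.3, is being modelled. Record the change in SAP Section 4.

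The cost is some SAP wording and a modest amount of code, with more care needed for PROC NLIN. No new data are required. There are two downsides. Subjects without a MultiHance CNR enter only the sensitivity fit. In the P03277-first sequence the covariate is measured after dosing, so its independence of dose relies on the washout of 2 to 14 days; the SAP should say so.

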## 7.1 Primary Criterion

The primary criterion (off-site read) is calculated by subject, and by independent blinded reader in a centralized procedure (off-site readers), in averaging the Contrast to Noise Ratio (CNR) for maximum 3 enhanced lesions. Only lesions detected by both MRIs after lesion tracking will be used. The evaluation will be done on combined images sets (1a, 2) and (1b, 3).

CNR is a variable derived for each lesion, from the Signal Intensity (SI) measurement. CNR will be calculated according to the following formula:

$$CNR = \frac{SI_{lesion} - SI_{ht}}{SD_{noise}}$$

where,

$SI_{lesion}$  = the SI in the Region Of Interest (ROI) in the lesion

$SI_{ht}$  = the SI in the ROI in healthy tissue (brain or spinal cord)

$SD_{noise}$  = standard deviation of background noise.

The SI measurement will be performed by the independent blinded readers on the pre and post-injection, axial 3D T1 weighted Gradient Echo (GRE) for brain and sagittal T1-weighted Spin-Echo (SE) or Turbo Spin-Echo (TSE) for spine, sequences. The post CNR value will be normalized by the pre-CNR (baseline) value.

Measurements of the SI of the lesion are to be made on the best representative images of the pathology, along with the SI of normal brain (white or gray matter) or spinal cord tissue, and of the image background.

 CONFIDENTIAL	Protocol No. GDX-44-004 Version No. 2.0 (Protocol including amendment n°1) Date: 11 July , 2016	 Page 35 / 84
---------------------------------------------------------------------------------------------------	----------------------------------------------------------------------------------------------------------	-----------------------------------------------------------------------------------------------------

These images will be selected according to the following:

- Up to 3 most representative lesions (largest enhancing lesion) will be measured separately.
- The lesion must have a size of at least 5 mm (long axis) to avoid partial volume averaging.
- The ROI for a lesion will encompass a homogeneous area within the lesion as large as possible.

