### 9.2.2 *MRI sequences*

The same parameter setting must be used for unenhanced images and for contrast-enhanced images in each subject (i.e., axial 3D T1 weighted GRE for brain and sagittal T1-weighted SE/TSE for spine).

The required sequences and parameters for P03277 and MultiHance® per subject should be identical as follows:

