### 3. STATISTICAL METHODS

### 3.1. General considerations

After the database lock, the statistical analysis will be performed by Inferential under the supervision of [name], Guerbet biostatistician, on the basis of the present document. A quality control of the statistical analysis will be performed to ensure the reliability of the results.

Thorough description of all parameters reported will be presented separately by group. Summary tabulated results will be provided by group and assessment time, if relevant or they will be replaced by the corresponding individual data listings if too few subjects are concerned.

Tabulations of quantitative parameters will include the following summary statistics: number of subjects, mean, SD, minimum, median and maximum. If for a given parameter, the raw value has been collected with  $x$  decimal places, the mean, median and SD will be rounded to  $x+1$  decimal places, while the minimum and maximum values will be tabulated as reported with  $x$  decimal places.

Tabulations of frequencies for categorical data will include all possible categories and will display the number of observations in a category as well as the percentage (%) relative to the respective group. Percentages will be rounded to one decimal place. The category missing will be displayed only if there are actually missing values. Percentages will be calculated on the total of non-missing recorded categories.

For safety analyses, the baseline value will be defined as the last available value prior to administration of the Investigational Medicinal Product (IMP). For the primary analysis of the primary efficacy criterion, the baseline value will be the pre CNR measurement for unenhanced lesions for each contrast agent period.

All statistical tests will be performed at the significant threshold of 2.5% one-sided. P-values will be displayed with 4 decimal places.

SAS® version 9.2 will be used for all descriptive summaries and inferential analyses.

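### The exploratory Emax fit in SAP 5.5.3.1 is saturated on four non-zero doses, leaves the measured pre-contrast CNR unused, and suggests a lambda start with the wrong units (minor)

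*SAP*

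**What the plan says.** SAP 5.5.3.1 states: "The relationship between doses and CNR will be explored by two modeling approaches on all data observed under P03277". One approach is a straight line in dose. The other is g(dose) = E0 + Emax·dose^lambda / (ED50^lambda + dose^lambda), fitted per off-site reader in PROC NLIN with "parms E0 = xxx Emax = xxx ED50 = xxx lambda = xxx". No parameter is fixed or bounded, and no convergence or fallback rule is given. Both models define E0 as the response with no dose, and both MODEL statements contain dose alone. A comment on starting values adds that "in particular, lambda may be retrieved from" the estimated slope in the preceding PROC REG. As to reporting: "Results from these models will be displayed in tables containing estimates and in figures".

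On the pre-contrast CNR:
- SAP 3.1, for the primary analysis: "the baseline value will be the pre CNR measurement for unenhanced lesions for each contrast agent period".
- SAP 3.4: it "will be included as covariate in the statistical models for the primary and supportive analyses of the primary criterion". The dose-response models sit in 5.5.3, under additional analyses, so this sentence does not reach them.
- Protocol 7.1: "The SI measurement will be performed by the independent blinded readers on the pre and post-injection" sequences.
- Protocol 9.2.2: "The same parameter setting must be used for unenhanced images and for contrast-enhanced images in each subject".

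**The concern.** Four free parameters on four dose means leave nothing with which to check the curve's shape. E0 has to be inferred from doses of 0.025 mmol/kg and above, although the trial measures the quantity that E0 describes. An unstable E0 carries over into Emax, ED50 and lambda, and all of them will be tabulated for a stated secondary objective (SAP 1.1).

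Separately, lambda is a unitless exponent, whereas the PROC REG slope is in CNR per mmol/kg. The same slope is 1000 times smaller if dose is in µmol/kg, so it cannot be a sensible start for lambda. At stake is the credibility of the reported estimates, and possibly a spurious step-shaped curve.

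**Working it through.** The plan states no precision target for this fit, so there is no figure of its own to reproduce. From SAP 3.3 I take 50 evaluable subjects per dose and SD 3.01, assuming that this planning SD applies to post-contrast CNR. All curve values below are assumptions, because the documents give none.

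**1. Count.**
- As written: 4 doses - 4 parameters = 0 df for lack of fit. Pure error keeps 4 × 50 - 4 = 196 df, and the Jacobian has rank 4.
- Pre-contrast CNR as dose 0: 5 levels - 4 parameters = 1 df.
- Post minus pre with E0 = 0: 4 doses - 3 parameters = 1 df.

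**2. Asymptotic precision.** Covariance = SD²·(J'J)⁻¹, at E0 1, Emax 15, ED50 0.1, lambda 1 (dose means 4, 6, 8.5, 11). Dose 0 is entered as 200 independent records with the same SD.

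| SE | E0 | Emax | ED50 | lambda |
|---|---|---|---|---|
| As written | 8.7 | 24.9 | 0.125 | 1.84 |
| With dose 0 | 0.21 | 5.3 | 0.077 | 0.33 |
| lambda fixed at 1, no dose 0 | 1.53 | 1.69 | 0.060 | – |

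The 0.21 is essentially 3.01/√200. Over five assumed curves the SE of E0 falls from 1.2–16.5 to about 0.21.

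**3. Simulated estimates.** Least squares by grid search (ED50 0.001–20, lambda 0.2–40), with pre-contrast SD half the post-contrast SD and correlation 0.5.
- E0 1, Emax 15, ED50 0.05, lambda 1, SD 3.01: the 5th to 95th percentiles of E0 are about -54 to 6 as written and 0.8 to 1.2 with dose 0. The lower end as written depends on the search limits.
- Same scenario, ED50 below 0.025: 31% as written, 0% with dose 0. ED50 above 0.2: 9% and 10%.
- E0 3, Emax 10, ED50 0.1, lambda 1, SD 5: ED50 above 0.2 rises from 26% to 38%. Other shallow-curve or large-SD settings gave 22% to 33% and 28% to 43%.

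**4. The curve within 0.025–0.2.** Over 36 Emax scenarios, median RMSE is 0.29–0.60 CNR units as written and 0.27–0.55 with dose 0. If the truth is not a sigmoid Emax through the pre-contrast value, dose 0 can do harm:
- dose means 6, 7, 12, 13 with pre-contrast -3: median RMSE at the studied doses rises from 0.40 to 0.92;
- dose means 6, 10, 13, 11 with pre-contrast 1: it rises from 0.78 to 0.86.

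**5. The lambda start.** Slope = Σ(d - d̄)y / Σ(d - d̄)². For the means in step 2, d̄ = 0.09375, the numerator is 0.684 and the denominator 0.01797, giving 38.1 CNR per mmol/kg. With ED50 0.05 or 0.1 and lambda 1, 1.5 or 2, the slope is 37.0 to 62.9 for Emax 15. It scales with Emax, so the low end for Emax 10 is 37.0 × 10/15 = 24.7.

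The gradient is ∂g/∂lambda = Emax·u(1 - u)·ln(d/ED50), with u = d^lambda/(ED50^lambda + d^lambda). At Emax 15 and ED50 0.07, its largest absolute value at any studied dose is:
- lambda 1: 3.0;
- lambda 2: 1.5;
- lambda 37: 0.00002. At d = 0.05, (0.05/0.07)^37 ≈ 4 × 10⁻⁶, times 15 × 0.336.

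At lambda 37 the curve equals E0 at the two lower doses and E0 + Emax at the two upper doses. Slope-seeded fits with two other optimizers ended at lambda above 10 in anywhere from 0 to 100% of trials, depending on algorithm, ED50 start and curve. Neither optimizer is PROC NLIN.

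**The case against.** The strongest reply is that little depends on this fit. It is an additional, exploratory analysis. Protocol 7.2.6 and 12.3 planned a graphical mean profile, with a model only as an option. No SAP rule uses E0, ED50 or lambda, and dose selection (SAP 5.5.1.5) is a benefit/risk choice among the four studied doses. If the Emax form holds, the plotted curve hardly changes. This stands, and it sets the severity.

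A saturated mean curve is not in itself an error: the SAP plans no lack-of-fit test, and the linear fit alongside has 4 - 2 = 2 such df. A reader might infer that the Emax model cannot be estimated. Rank 4 and about 196 pure-error df show otherwise.

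The omission of dose-0 records is inferred. The dataset name is masked, the response variable is not defined in 5.5.3.1, and Protocol 7.1 says post-contrast CNR is to be normalized by the pre-contrast value. The primary code in SAP 5.5.1.3 holds response and baseline as separate variables. That favours reading the response as raw post-contrast CNR but does not settle it.

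The lambda comment is permissive and concerns only a starting value. A reader might infer that PROC NLIN will return a false step curve. The documents do not support a rate for that; the unit mismatch itself remains.

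**Conclusion.** The point holds as a minor one. As its text and code read, SAP 5.5.3.1 fits a saturated four-parameter curve, extrapolates E0 when the corresponding measurement is already collected, and suggests a start for lambda in the wrong units.

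Using the pre-contrast CNR would give a well-determined E0 and far fewer ED50 estimates below 0.025. It would not reliably reduce ED50 estimates above 0.2 for shallow curves or a large SD, so it should not be presented as a cure for ED50. Within 0.025–0.2 the curve changes little if the Emax form is right, and can fit worse if it is not.

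A reader might go further and infer that the choice of dose is compromised. The documents do not support that: the Holm tests and the comparison among the four studied doses do not use these estimates.

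The sizes rest on assumed curves, 50 subjects per dose, the planning SD of 3.01 (5 in some settings), and an assumed pre/post SD ratio and correlation. The units argument and the parameter count need none of these.

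**What to change.** 1. Delete the comment that takes lambda from the PROC REG slope. Start lambda from a small grid around 1 to 2 and keep the fit with the lowest residual sum of squares.
2. Pre-specify an Emax fit that uses the pre-contrast CNR, reported beside the fit as written. Either model post minus pre with E0 = 0, or enter pre-contrast CNR as dose-0 records with a subject effect (for example in PROC NLMIXED). In the second form, code the dose term as 0 at dose 0, because the derivative for lambda contains log dose. Put the linear model on the same basis. Check fitted against observed dose means, given the possible loss of fit in the studied range.
3. Name lambda = 1 as the sensitivity fit, or as the fallback if the chosen form does not converge.

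The cost is SAP text and a few lines of code, with no new data. Post minus pre drops subjects without a pre-contrast CNR at the P03277 examination, since SAP 5.2.1 requires both measurements from only one MRI. The dose-0 form keeps those subjects but needs a nonlinear mixed procedure; the simulations above ignored within-subject correlation in the fit, so its exact gain has not been measured.
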